1.0 PROTOCOL SUMMARY

1.1 Synopsis

TITLE:	Yttrium-90 Radiation Segmentectomy versus Stereotactic Body Radiation Therapy (SBRT) for the Treatment of Early Stage Hepatocellular Carcinoma (HCC): A Pilot Study
STUDY DESCRIPTION:	The proposed study is a single site, prospective, randomized pilot study to assess the feasibility of recruitment of patients into a trial evaluating the efficacy and tolerability of selective transarterial Y90 radioembolization (radiation segmentectomy) versus stereotactic body radiation therapy (SBRT) for solitary early stage (≤ 3cm) hepatocellular carcinoma (HCC).
OBJECTIVES:	Primary Objective: 1. To assess feasibility as measured by screen failures and rate of recruitment into a randomized trial comparing RS and SBRT Secondary Objectives: 1. To evaluate the proportion of patients with any toxicities (≥ grade 4) using CTCAE between RS and SBRT for patients with small (≤3 cm) solitary hepatocellular carcinoma (HCC). 2. To evaluate the mean change in hepatobiliary function, as measured 3 months after treatment using a functional HIDA scan, between RS and SBRT for patients with small (≤3 cm) solitary hepatocellular carcinoma (HCC). 3. To evaluate the mean change in patient-reported outcomes from baseline, at 1, 3 and 6 months, between RS and SBRT, for patients with small (≤3 cm) solitary hepatocellular carcinoma (HCC), using the Functional Assessment of Cancer Therapy- General (FACT-G) and COST FACIT questionnaires. 4. To evaluate the disease-free survival (DFS) rates of RS and SBRT at 2 years using mRECIST on CT or MR for patients with small (≤3 cm) solitary hepatocellular carcinoma (HCC). 5. To evaluate time-to-secondary treatment (TTST) between RS and SBRT for patients with small (≤3 cm) solitary hepatocellular carcinoma (HCC) up to 2 years after initial treatment. 6. To measure the objective response rate (ORR) of radiation segmentectomy (RS) and stereotactic body radiation therapy (SBRT) as measured at 6 months using mRECIST (appendix IV) for patients with small (≤3 cm) solitary hepatocellular carcinoma (HCC) to better allow for an appropriately powered trial evaluating the efficacy of these treatments

[figure not shown]
Protocol Version: 15DEC2021

5

ENDPOINTS:	Primary Endpoint: Recruitment rates measured at 6 and 12 months and screen failures assessed by the detailed screen failure form at the time patients are approached for enrollment to ascertain specific reasons why patients may choose not to enroll Secondary Endpoints: 1. Laboratory (CBC, CMP, INR)/clinical toxicities measured using CTCAE version 5.0 2. Change in % radiotracer extraction from baseline, on functional HIDA scan, 3 months after treatment 3. Change in FACT-G and COST FACIT from baseline at 1, 3, and 6 months 4. ORR at 6 months after completion of treatment using mRECIST on multiphase CT or MR.
STUDY POPULATION:	20 (up to 10 enrolled per arm) male or female patients with small (\leq 3 cm) solitary hepatocellular carcinoma with relatively preserved liver function (CPS \leq 7)
PHASE:	N/A
DESCRIPTION OF STUDY INTERVENTION:	The SBRT arm of the trial will involve standard SBRT delivered over 3-5 fractions as tolerated with dose/total therapy adjusted as needed for safety. The RS arm of the trial will involve a planning arteriogram followed by selective transarterial delivery of Yttrium-90 into the segmental (≤2) artery supplying the tumor. Administered activity will be an amount prescribed to deliver a dose ≥200 Gy to the perfused tissue.
STUDY DURATION:	Estimated 12 months for accrual with another 24 months needed to complete secondary endpoints. 6 more months for data analysis. Total: 66 months
PARTICIPANT DURATION:	24 months from therapy completion. (approximately 26 months from randomization)

Protocol Version: 15DEC2021

1.2 Schema

1.3 Schedule of Events

Procedures	Enrollment / Baseline	Pre-Treatment	Intervention /Treatment	1 month visit	3 month visit	6 month visit	9 month visit	12 month visit	15 month visit	18 month visit	21 month visit	24 month visit
		Within 30 days from enrollment	Within 45 days of pre- treatment visit procedures	30 days from end of treatment (+/- 15 days)	90 days from end of treatment (+/- 30 days)	180 days from end of treatment (+/- 30 days)	270 days from end of treatment (+/- 30 days)	360 days from end of treatment (+/- 30 days)	450 days from end of treatment (+/- 30 days)	540 days from end of treatment (+/- 30 days)	630 days from end of treatment (+/- 30 days)	720 days from end of treatment (+/- 30 days)
Informed consent	Х											
Demographics	Х											
Medical history	Х											
Randomization	Х											
Pregnancy Test (urine or serum) ^G	х											
Planning/mappin g arteriogram ^F		Х										
CT simulation ^E		Х										
Administer Study intervention ^c			х									
Physical exam	Х			Х	Х	х	х	х	х	х	х	х
Vital signs	Х			Х	Х	х	х	х	Х	х	х	х
Performance status	Х			Х	Х	Х	х	х	х	х	Х	х
Lab tests ^A	Х		Х	Х	Х	Х	х	х	х	х	х	Х
Adverse event review and evaluation ^H	Х	х	х	х	х	х						
Radiologic/Imagin g assessment ^D	Х				Х	Х	Х	х	х	х	х	х
Complete Case Report Forms (CRFs)	х		х	Х	Х	х	Х	х	х	х	Х	Х

Functional Hepatobiliary Scan		Хв		Х				
Patient Reported Outcome Measures (FACT- G, COST FACIT)	Х		Х	х	х			

A Complete Blood Count (CBC), Comprehensive Metabolic Profile (CMP), International normalized ratio (INR), and Alpha Fetoprotein (AFP). AFP will only continue to be drawn after baseline if initially elevated (>10 ng/mL)

B Baseline functional hepatobiliary scan should be completed after enrollment, but prior to start of treatment.

C SBRT Arm: Child Pugh A patients will receive a prescription dose of either 5000cGy in 5 fractions delivered every other day or 4800cGy in 3 fractions delivered twice weekly. Child Pugh B patients will receive a prescription dose of 4000cGy in 5 fractions delivered every other day. Patients will be seen at least once per week by a clinician to grade toxicities, with on-treatment labs (CBC, CMP, INR) each week. RS Arm: After planning arteriogram, subjects will return within 30 days to receive a single administration of Yttrium-90 into the segmental (≤2) artery supplying the tumor. Administered activity will be an amount prescribed to deliver a dose ≥200 Gy to the perfused tissue.

D Multi-phase contrast enhanced CT or MR of the abdomen. Baseline imaging should be obtained within 3 months of enrollment

E To be performed in patients receiving SBRT only prior to treatment

F To be performed in patients receiving RS only prior to treatment

G Required only in women of child bearing potential

H Adverse events will be reviewed and collected from the time of informed consent until 30 days after the 6 month visit. See section 12.4 for details

I SBRT arm only: Patients will be seen at least once per week by a clinician to grade toxicities during treatment, with on-treatment labs (CBC, CMP, INR) each week.

Protocol Version: 15DEC2021

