7.0 STUDY INTERVENTION

7.1 Study Interventions

There are two comparative intervention arms, both of which are currently standard-of-care.

7.1.1 Selective transarterial radioembolization (Radiation Segmentectomy (RS)):

This therapy arm involves two separate steps, a planning/mapping arteriogram and a therapy delivery. The planning arteriogram will be performed to confirm arterial anatomy is acceptable for RS (\leq 2 segment delivery) and that lung shunting is not too high to preclude treatment with RS. Once confirmed, patients will return for RS (within 45 days of mapping). Dose will be calculated based off the desired treatment volume using pre-treatment cross-sectional imaging. The desired segmental dose will be calculated to be \geq 200Gy. RS will be performed by one of three separate interventional radiologists with experience in radioembolization. Actual administered activity and location of dose administration will be recorded.

7.1.2 Stereotactic Body Radiation Therapy (SBRT):

SBRT will be delivered with linear accelerator-based photon beams with either fixed angle non-coplanar fields or dynamic arcs. For treatment planning, CT simulation with triple phase IV contrast would be performed in the treatment position (supine, arms up). Tumor motion management would be assessed with 4D CT through the breathing cycle. Abdominal compression or breath-hold may be used at physician discretion for diaphragmatic excursion of 1cm or more. Available pre-treatment diagnostic imaging will be fused with the planning CT by deformable registration to assist in target and normal tissue delineation. An internal target volume (ITV) will be generated to account for tumor movement during breathing cycle. Finally, a planning target volume (PTV) will be an expansion of 3-5mm from the ITV. For Child Pugh A patients, prescription dose will either be 5000cGy in 5 fractions delivered every other day or 4800cGy in 3 fractions delivered twice weekly. For Child Pugh B patients, prescription dose of 4000cGy in 5 fractions delivered every other day. Inverse planning will be used. 95% of the PTV or more will receive at least 100% of the prescription dose. Normal tissue dose constraints for each dose level will be respected with acceptable deviations permitted as outlined in appendix VII. Patients will be seen at least once per week by a clinician to grade toxicities, with on- treatment labs (CBC, CMP, INR) each week.

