8.0 STUDY EFFICACY AND SAFETY ASSESSMENTS

8.1 Efficacy Assessments

Patients will initially be flagged as potential candidates for the trial following a local tumor board discussion that the location and overall clinical picture would allow for either treatment as a viable option. Once tumor board agreement has been obtained, patients will be scheduled for a multi- disciplinary clinic visit where they will have a complete clinic visit with interventional radiology and radiation oncology back-

to-back. If after these visits patients fulfill inclusion/exclusion criteria, they will immediately thereafter be approached by a research coordinator and enrollment will be attempted.

If patients decline participation, a detailed screen fail form will be filled out to try and best ascertain reasons for declined participation. If the patient agrees to participate, they will be enrolled and randomized (as described above) at that time.

A virtual/telehealth provision will be permitted for all follow-up visits. Since the virtual visit does not allow for effective physical exam of all body systems and vitals are unable to be obtained virtually, these elements will not be required during virtual visits. Labs will be obtained, however, as well as required imaging. If questionnaires are required during a virtual/telehealth visit, they may be administered via REDCap survey.

Baseline: Labs, medical history/physical exam and PROs questionnaires will be obtained during the initial clinic visit prior to randomization. Subjects will be required to have an MRI or CT of the abdomen within 3 months of enrollment.

Pre-Treatment: Patients will return for functional hepatobiliary scan and treatment planning procedures prior to treatment (≤ 30 days from enrollment)

Treatment: Patients will undergo treatment as described above in Section 7.1.

Follow Up Visits:

One month (± 15 days) after treatment completion patients will return for a clinic visit with labs (CBC, CMP, INR, AFP (if elevated at baseline)), physical exam, and PROs using FACT-G and COSTFACIT.

Three months after treatment completion (± 30 days) patients will return for a clinic visit with labs (CBC, CMP, INR, AFP (if elevated at baseline)), physical exam, and PROs using FACT-G and COST FACIT. Patients will also undergo multi-phase contrast enhanced CT or MR of the abdomen and functional hepatobiliary scan.

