10.5.3 Analysis of the Secondary Endpoint(s)

The secondary research questions to be addressed are as follows:

- 1. To compare the proportion of any toxicities (≥ grade 4) using CTCAE between RS and SBRT for patients with small (≤3 cm) solitary hepatocellular carcinoma (HCC).
 - The proportion of patients with toxicities will be provided along with corresponding 95% confidence intervals. Toxicity rates will be compared using a Fisher's Exact Test.
- 2. To compare the mean change in hepatobiliary function, as measured 3 months after treatment using a functional HIDA scan, between RS and SBRT for patients with small (≤3 cm) solitary hepatocellular carcinoma (HCC).
 - A two-sample t-test will be used to analyze mean changes in liver function as measured by functional HIDA scan.
- 3. To compare the mean change in patient-reported outcomes from baseline, at 3 and 6 months, between RS and SBRT, for patients with small (≤3 cm) solitary hepatocellular carcinoma (HCC), using FACT-G and COST FACIT.
 - A two-sample t-test will be used to analyze mean changes in patient reported outcomes as measured using FACT-G and COST FACIT.
- 4. To compare the disease-free survival (DFS) rates of RS and SBRT at 2 years using mRECIST on CT or MR for patients with small (≤3 cm) solitary hepatocellular carcinoma (HCC).
 - DFS rates will be compared using Kaplan-Meier estimates with a log rank analysis.
- 5. To compare time-to-secondary treatment (TTST) between RS and SBRT for patients with small (≤3 cm) solitary hepatocellular carcinoma (HCC) up to 2 years after initial treatment.
 - TTST rates will be compared using Kaplan-Meier estimates with a log rank analysis.

6. The proportion of patients with ORR at 6 months will be provided along with corresponding 95% confidence intervals. ORR rates will be compared using a Fisher's Exact Test.

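### During the 8-9 day SBRT course only SBRT patients have weekly toxicity grading and labs, so the between-arm toxicity rates are unequally ascertained; the effect is probably small

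*Combined protocol and SAP*

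**What the plan says.** **On-treatment monitoring.** Footnote I of the Schedule of Events (1.3) states: "SBRT arm only: Patients will be seen at least once per week by a clinician to grade toxicities during treatment, with on-treatment labs". Section 7.1.2 repeats it for SBRT: "Patients will be seen at least once per week by a clinician to grade toxicities, with on- treatment labs (CBC, CMP, INR) each week". Footnote C and section 9.1 are consistent with this. Section 7.1.1, on RS, has no counterpart.

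**Length of treatment.** For Child-Pugh A patients on SBRT, the "prescription dose will either be 5000cGy in 5 fractions delivered every other day or 4800cGy in 3 fractions delivered twice weekly" (7.1.2). Child-Pugh B patients also receive five fractions on alternate days. In the RS arm, "subjects will return within 30 days to receive a single administration of Yttrium-90 into the segmental" artery (1.3, footnote C).

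**After treatment.** The first follow-up visit is set at "30 days from end of treatment (+/- 15 days" in the Schedule of Events. Section 8.1 agrees: "One month (± 15 days) after treatment completion patients will return for a clinic visit with labs". Neither place distinguishes the arms.

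**Event collection.** The schedule row "Adverse event review and evaluation" is marked at baseline, pre-treatment, treatment, and 1, 3 and 6 months. Its footnote H has no arm restriction. Under 13.3, adverse events are recorded from consent, patients are asked at each visit about the interval since the previous one, and events may also be found through medical care or chart review.

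**Endpoint and test.** Section 4.2 item 1 counts laboratory (CBC, CMP, INR) and clinical toxicities of grade 4 or higher that are at least possibly treatment-related, through six months after treatment. It does not say when counting starts. Section 10.5.3 item 1 states: "Toxicity rates will be compared using a Fisher's Exact Test". Neither 10.5.3 nor 10.5.4 says which assessments feed that comparison.

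**The concern.** A laboratory toxicity enters the data only if blood is drawn. The panel drawn weekly in SBRT is the same panel that defines the laboratory part of the endpoint, and the weekly draws exist in one arm only. If true toxicity were equal, a grade 4 value that appeared and resolved within the first days would be counted in SBRT and could go unseen in RS. Asking the patient later, or reading the chart, cannot recover a value that was never measured.

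What is at stake is the descriptive output. Sections 2.1 and 2.2 say that comparative safety data are limited and that no head-to-head comparison exists, so the arm-specific rates and confidence intervals may be read as early comparative evidence. With 10 patients per arm, each additional patient with an event moves an arm's rate by 10 points. Section 8.2 lists liver toxicity among the most common expected toxicities, and the blood panel is one of the ways it is detected.

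**Working it through.** The plan gives no alpha, power or toxicity rate for this comparison, so there is no figure to reproduce. Section 10.3 sets 20 patients, up to 10 per arm, for feasibility.

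**Step 1: number of extra looks.**
- Five fractions on alternate days: 1 + 4 × 2 = 9 days.
- Three fractions twice weekly: about 8 days.
- Weekly grading and labs over 8-9 days: about two looks.
- RS: one administration, so treatment ends the day it is given and there is no on-treatment period.

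**Step 2: where the schedules differ.** The first follow-up visit falls at 30 ± 15 days, that is day 15 to day 45, counted from end of treatment in both arms. SBRT therefore has the same unscheduled gap after its last fraction as RS has after its dose. The 1, 3 and 6 month visits are common. The difference is confined to 8 or 9 days of a treatment-plus-180-day window: 8/188 = 4.3% to 9/189 = 4.8%.

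**Step 3: which events are exposed.** Clinical events of grade 4 or higher are largely protected by continuous collection, inquiry at each visit and chart review. A laboratory abnormality still present at the 1 month draw is found in both arms. What remains is a related laboratory value of grade 4 or higher that resolves before that draw.

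**Step 4: illustrative size.** Let p be the true patient rate, equal in both arms, and m the share of events missed in RS only. The apparent rates are p in SBRT and p(1 − m) in RS, so the false excess is p × m. Neither p nor m is in the documents; the values below are assumptions. The percentage in each cell is the exact probability that Fisher's test gives p < 0.05 with SBRT worse, at 10 per arm (two-sided 0.05 assumed).

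| True rate p | m = 0 | m = 25% | m = 50% |
|---|---|---|---|
| 5% | 0 points; 0.004% | 1.25 points; 0.004% | 2.5 points; 0.005% |
| 10% | 0 points; 0.06% | 2.5 points; 0.08% | 5 points; 0.10% |
| 20% | 0 points; 0.38% | 5 points; 0.68% | 10 points; 1.2% |
| 30% | 0 points; 0.59% | 7.5 points; 1.5% | 15 points; 3.4% |

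In patients per arm of 10, 2.5 points is 0.25 patients and 10 points is one patient. The test itself hardly responds: 4/10 v 0/10 gives p = 0.087, and significance needs at least 5/10 v 0/10 (p = 0.033) or 7/10 v 1/10 (p = 0.020).

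**The case against.** The strongest case against is that little is exposed. The endpoint takes only events of grade 4 or higher judged at least possibly related, clinical events are collected continuously, and the asymmetry lasts 8-9 days. Section 9.1 regards toxicity severe enough to stop SBRT as unexpected. The comparison is an unpowered secondary one. All of this stands, and it limits the size. It does not remove the gap, because a blood value that was never drawn cannot be recovered.

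A second objection also has force: restricting the comparison to common visits drops real acute SBRT toxicity and could favour SBRT. For that reason the common-visit comparison should sit beside the all-assessments one, not replace it.

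Four stronger readings are tempting, and the documents do not support them.

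- *RS has nothing scheduled until day 15-45.* Adverse event review is marked at the pre-treatment and treatment columns without arm restriction, and labs are marked at the treatment column. In the available text the anchor of footnote I cannot be seen, so whether that lab mark covers RS is uncertain; the adverse event mark is not in doubt.
- *A false excess of 4 to 14 points.* Taking 3 post-dose looks in RS and 5 in SBRT, 1 − (1 − q)^k gives 5.9% v 9.6% at q = 2%, 14.3% v 22.6% at 5% and 27.1% v 41.0% at 10%. This assumes independent draws, the same q at every time point, no persistence between draws and RS treatment-day labs taken before the dose. No q is given, and at q = 0.5% the same formula gives 1.5% v 2.5%.
- *The test would falsely condemn SBRT.* The largest probability in the table is 3.4%, under a deliberately extreme assumption.
- *The only between-arm safety comparison is compromised.* Table 1 gives the HIDA comparison the same justification, harm to surrounding liver, and it is scheduled alike in both arms.

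**Conclusion.** The point holds in a limited form and is minor. Scheduled surveillance differs between the arms by about two gradings and two blood draws during the SBRT course, the toxicity comparison takes no account of it, and any resulting bias raises the SBRT rate relative to RS. The direction follows from the schedule. The size cannot be derived and is probably small, because it depends on how often a related laboratory value of grade 4 or higher appears and resolves before the 1 month draw. The consequence is for how the reported rates are read; the primary feasibility objective is unaffected.

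The conclusion assumes that SBRT on-treatment findings count toward the endpoint, which the wording in 4.2 and 10.2.2 leaves open, and that RS patients have no routine post-dose labs before the 1 month visit beyond those the protocol lists.

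**What to change.** In 10.5.3 item 1:

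1. Keep the all-assessments comparison and label its rates as unequally ascertained.
2. Beside it, report laboratory toxicity by arm from the visits common to both arms (1, 3 and 6 months), and name this as the like-for-like comparison.
3. Tabulate SBRT on-treatment laboratory and grading findings separately.
4. State when counting starts, and count clinical events from the same starting point in both arms.

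In 1.3, state which mark footnote I applies to.

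The cost is a paragraph of wording and one extra table, with no new visits or blood draws. The drawback is that the common-visit comparison omits acute on-treatment SBRT laboratory events; these remain in the all-assessments analysis and in the separate table.

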2.0 BACKGROUND AND RATIONALE

2.1 Study Rationale

Primary liver cancer is one of the five the most frequently diagnosed cancers in the world and is the second leading cause of cancer death worldwide. Early stage HCC (≤3 cm) is often treated by surgical resection with curative intent. Patients are often not candidates for surgery and there are multiple locoregional therapy options that exist as second line therapy options. Two of these options focus on directed radiation delivery to the tumors, either externally via SBRT or internally via transarterial radioembolization. There are currently limited data on differences in efficacy and safety between these modalities. At our institution, both of these treatments are offered as comparable first line options for unresectable HCC. A direct comparison of these two-radiation based locoregional therapies is therefore felt to be valuable. Unfortunately, the majority of published data with these treatments are retrospective, single institution studies. A direct comparison of the published results is made more difficult by the fact that most literature for radioembolization reports response rates using specific imaging response criteria (i.e. RECIST, mRECISCT, EASL) while most studies on SBRT report efficacy in terms of disease control rate. Given these limited data, with response rates reported using different criteria, a pilot study measuring ORR using the modified RECIST (mRECIST) Assessment for Hepatocellular Carcinoma criteria is proposed to better estimate the true ORR to help aid in the power calculation for a full trial.

